11.2.3 Serious Adverse Event (SAE)

A serious adverse event (SAE) is defined in line with (CFR - Code of Federal Regulations Title 21 Sec. 312.32) as any adverse experience that, in the view of either the Investigator or sponsor, meets any of the following criteria:

- Results in death
- Is life-threatening

(NOTE: Life-threatening means that the patient was at immediate risk of death from the reaction as it occurred, i.e., it does not include a reaction which hypothetically might have caused death had it occurred in a more severe)

- Requires inpatient hospitalization or prolongation of existing hospitalization

NOTE: In general, hospitalization means that the individual remained at the hospital or emergency ward for observation and/or treatment (usually involving an overnight stay) that would not have been appropriate in the physician's office or an outpatient setting. Complications that occur during hospitalization are AEs. If a complication prolongs hospitalization or fulfills any other serious criteria, the event is serious. When in doubt as to whether "hospitalization" occurred, the event should be considered serious.

- Results in persistent or significant disability/incapacity

(NOTE: The term disability means a substantial disruption of a person's ability to conduct normal life functions. This definition is not intended to include experiences of relatively minor medical significance such as uncomplicated headache, nausea, vomiting, diarrhea, influenza, or accidental trauma (e.g., sprained ankle) which may interfere or prevent everyday life functions but do not constitute a *substantial disruption*).

- Results in a congenital anomaly/birth defect
- Is an important medical event

(NOTE: An important medical event is an event that may not result in death, be life-threatening, or require hospitalization but may be considered a SAE when, based upon appropriate medical judgment, it may jeopardize the patient's wellbeing and may require medical or surgical intervention to prevent one of the outcomes listed in the definitions for SAEs. Examples of such medical events include allergic bronchospasm requiring intensive treatment in an emergency room or at home, blood dyscrasias or convulsions that do not result in patient hospitalization or the development of drug dependency or drug abuse).

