11.2.6 Adverse Events (AEs) of Special Interest (Sight-threatening Events)

The following adverse events are considered to be of special interest and by default shall be reported as SAEs (medically important criteria):

- AEs that caused a decrease in visual acuity of >30 ETDRS letters or > +0.6 LogMAR (compared with the last assessment of visual acuity at the last visit) lasting >1 hour
- AEs that caused a decrease in visual acuity to the level of Light Perception or worse lasting >1 hour
- AEs that required surgical intervention (e.g., conventional surgery, vitreous tap or biopsy with intravitreal injection of anti-infectives, or laser or retinal cryopexy with gas) to prevent permanent loss of sight
- AEs associated with severe intraocular inflammation (i.e., 4+ anterior chamber cell/flare or 4+ vitritis)
- AEs that, in the opinion of the Investigator, may require medical intervention to prevent permanent loss of sight.

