7.1 Analysis Sets

A patient will be defined as *screened* after the signature of the informed consent, regardless of the completion of all the screening procedures. A patient will be defined as screen failure, if he was screened but not enrolled in the study.

Enrolled Set:

A patient will be defined as *enrolled* in the study if he/she is randomized. This analysis set will be used for demographic, baseline and background characteristics.

If not stated otherwise, analyses based on the Enrolled Set will be summarized by the treatment randomized.

Safety Set (SAF):

The Safety Set will be defined as all enrolled patients who receive at least one dose of the investigational medicinal product (IMP). *This analysis set will be used for the safety analysis.* All analyses based on the SAF will be summarized by the treatment received.

Full Analysis Set (FAS):

The Full analysis set will be defined as all patients in the SAF, who have receive at least one dose of the IMP in the study eye and who have at least one post-baseline Sande score assessment or another post-baseline efficacy measurement in the study eye. This analysis set will be used for efficacy analyses. All efficacy analyses based on the FAS will be summarized by the treatment randomized.

Per Protocol Set (PPS):

The Per Protocol set will be defined as *all patients in the FAS who fulfill the study protocol requirements in terms of investigational medicinal product intake and collection of primary efficacy data and with no major deviations that may affect study results. This analysis set will be used for supportive efficacy analysis.* All efficacy analysis based on the PPS will be summarized by the treatment randomized.

After all patients have completed study and prior to database lock, a blinded data review meeting (BDRM) will be performed to assign patients to analysis sets. Details of BDRM will be specified in a separate BDRM-plan.

The BDRM plan will consider the following criteria for exclusion of a patient from the PPS:

- *lack of compliance with investigational medical product administration*

A compliance below 80% or greater than 120% will lead to exclusion from the PPS (compliance definition please refer to section 8.2.5).

- *exposure to an IMP dose different from the one assigned to the patient*

- *missing primary efficacy data*
- *failure to satisfy any inclusion/exclusion criteria (eligibility violations)*
- *intake of prohibited medications*

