Moreover, a review of protocol deviations and potential consequences for the analysis will be evaluated during the BDRM. The results of the BDRM will be summarized in BDRM Minutes, which will be finalized before unmasking.

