8.2.8 Safety Variables

Adverse Events (AE)

AE data are collected on the 'Adverse Events' eCRF page. Corrective medications or procedures due to an AE are documented on the eCRF pages 'Prior and Concomitant Medications' and 'Corrective Procedures Related to AE' respectively.

The AE Description (Investigator term) will be coded to a Preferred Term (PT) and a System Organ Class (SOC) using MedDRA, Version 19.1.

Based on the information provided on the 'Adverse Events' eCRF page, the following definitions will be utilized:

- An ocular event will be identified, if the question 'Is this an ocular event?' is answered 'Yes'.
- An AE with missing severity will be counted as severe.

- A Serious Adverse Event (SAE) is any adverse event where the question ‘Is the event serious?’ has been answered as ‘Yes’. If this question is not answered the event will be considered as ‘Serious’ for analysis purposes.
- *The following adverse events are considered to be of special interest (AESI) and by default shall be reported as SAEs (medically important criteria):*
 - *AEs that caused a decrease in visual acuity of >30 ETDRS letters or > +0.6 LogMAR (compared with the last assessment of visual acuity at the last visit) lasting >1 hour*
 - *AEs that caused a decrease in visual acuity to the level of Light Perception or worse lasting >1 hour*
 - *AEs that required surgical intervention (e.g., conventional surgery, vitreous tap or biopsy with intravitreal injection of anti-infectives, or laser or retinal cryopexy with gas) to prevent permanent loss of sight*
 - *AEs associated with severe intraocular inflammation (i.e., 4+ anterior chamber cell/flare or 4+ vitritis)*
 - *AEs that, in the opinion of the Investigator, may require medical intervention to prevent permanent loss of sight.*

For analysis purposes, and AESI will be identified by ticked box ‘Medically significant or important medical condition’ in the eCRF section ‘SAE criteria’. This means in particular, that all AESIs will be considered as SAEs.

- An AE leading to premature withdrawal of the study treatment is defined as an AE where in the eCRF section ‘Action taken with study treatment’ the boxes ‘Withdrawn’ and ‘Definitely’ are ticked.
- An AE leading to study treatment interruption is defined as an AE where in the eCRF section ‘Action taken with study treatment’ the boxes ‘Withdrawn’ and ‘Temporarily’ are ticked.

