10.6 Safety Results

10.6.1 Adverse Events

10.6.1.1 Brief Summary of Adverse Events

Reporting of AEs is focused to treatment emergent AEs.

An overview of AEs, TEAEs, TEAEs during Treatment Period, TEAEs during Follow-up Period, TEAEs leading to premature withdrawal of the Study Treatment, TEAEs leading to study discontinuation, serious TEAEs, treatment related TEAEs, treatment related serious TEAEs, TEAEs of special interest and Mild, Moderate and Severe TEAEs will be given by study treatment and overall for patients in the SAF. For each events, the number and percentages of patients with at least one event as well as the total number of events will be provided.

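### SAP 8.2.8 identifies sight-threatening adverse events of special interest by a generic seriousness box, so other important medical events would be counted with them

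*SAP*

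**What the plan says.** Protocol 11.2.6 restricts AESIs to sight-threatening events and lists five criteria: two on loss of visual acuity, one on surgery to save sight, one on severe intraocular inflammation, and one on the investigator's opinion that intervention may be needed to save sight. It adds that these events "by default shall be reported as SAEs (medically important criteria"). SAP 8.2.8 repeats the five criteria and the reporting instruction.

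SAP 8.2.8 then gives the rule for the data: "For analysis purposes, and AESI will be identified by ticked box" "Medically significant or important medical condition" in the SAE criteria section of the eCRF. It adds that every AESI is therefore treated as an SAE. No further condition is attached.

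Protocol 11.2.3 explains what an important medical event is: "Examples of such medical events include allergic bronchospasm requiring intensive treatment in an emergency room or at home, blood dyscrasias or convulsions" that do not lead to hospitalization.

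The flag is used in SAP 10.6.1.1, where "TEAEs of special interest and Mild, Moderate and Severe TEAEs will be given by study treatment and overall for patients in the SAF", as numbers and percentages of patients and as numbers of events.

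**The concern.** The protocol's link runs one way: an event that threatens sight is to be reported as a medically important SAE. The SAP uses the converse and treats a medically important SAE as an event that threatens sight. The converse fails because the box is also the right place for serious events that have nothing to do with vision.

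What is at stake is the meaning of one row. Efficacy and safety together form the primary objective, and in an eye-drop trial a reader will take the AESI row as the count of sight-threatening events. SAP 10.6.1.2 and 10.6.1.3 plan no separate AESI table or listing, so this row is the only place where AESIs are displayed as such.

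**Working it through.** The plan states no figure to reproduce. The check is a comparison of rules, followed by the weight of a single case.

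**Does the rule admit an event that is not an AESI?** Take a convulsion after the first dose, without hospitalization, recorded as the protocol directs.

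1. Protocol 11.2.3: it is one of the named examples of an important medical event, so it is serious and the box is ticked.
2. SAP 8.2.8, treatment-emergent events: it began during the treatment period. The added requirement that the affected eye was treated applies only to ocular events, so it does not exclude the convulsion.
3. SAP 8.2.8, AESI rule: the box is ticked, so the event is an AESI. The SAP says that its AE definitions carry down to the sub-classes of AEs.
4. SAP 10.6.1.1: the event enters the row for treatment-emergent AESIs.
5. Protocol 11.2.6: if the convulsion has no consequence for vision, it meets none of the five criteria.

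The miscount needs no recording error; correct recording produces it.

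**Does anything visible remove it?** The AE page has an ocular yes/no item, but the AESI rule does not use it. SAP 7.1 says that "prior to database lock, a blinded data review meeting (BDRM) will be performed to assign patients to analysis sets" and that "a review of protocol deviations and potential consequences for the analysis will be evaluated during the BDRM". SAP 8.1 adds conformance with the visit schedule, and SAP 8.2.5 adds diary and other compliance data. None of these mentions AESIs. SAP 4.7 does not list the rule among the changes from the protocol.

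**Weight of one false case.** Inputs: 100 rhNGF and 50 vehicle patients planned (protocol 8.1, SAP 4.2), all assumed to be in the Safety Set.

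- rhNGF: 1/100 = 1.0 percentage point
- Vehicle: 1/50 = 2.0 percentage points
- Overall: 1/150 = 0.67 percentage points

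**Direction between arms.** Suppose there are no true AESIs and one false case unrelated to treatment. The difference (rhNGF minus vehicle) is +1.0 with probability 100/150 = 2/3, or −2.0 with probability 50/150 = 1/3. Its expectation is 2/3 × 1.0 − 1/3 × 2.0 = 0. Under that assumption the rule raises the level of the row and adds noise, without favouring an arm.

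**Traceability.** Any such event also appears by preferred term in the table of serious TEAEs (SAP 12, Table 14.3.1-5.1), and by patient in the full AE listing and the serious AE listing (SAP 10.6.1.3).

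**The case against.** The five criteria stand in the same bullet as the box rule. One can therefore read the box as a flag for events already so defined, not as a wider definition. This reading is possible but weak: SAP 8.2.8 uses ticked boxes as complete identification rules elsewhere, for example for events before treatment, and a programmer has nothing else to apply. It remains true that the eCRF, the data review plan and the table shells were not available. Any of them might contain a specify field, a review step or a footnote that resolves the matter.

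It can also be said that over-inclusion suits the section's cautious conventions, under which missing severity counts as severe, missing seriousness as serious and missing relationship as related. Those conventions deal with missing answers. Here the answers are complete and the label is wrong.

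The objection about weight stands. AESIs are not an endpoint, and no test or decision rule depends on them. The per-case figures would hold for any misclassified event and say nothing about how many to expect.

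A reader might also infer that the rule will miss true sight-threatening events. That happens only if the box is left unticked, which would depart from the default reporting in protocol 11.2.6. It is a conditional risk, not a consequence of the rule as written.

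**Conclusion.** The point holds as a minor error in a stated rule. Followed as written, SAP 8.2.8 would count treatment-emergent important medical events that do not threaten sight in the row for AESIs. One false case adds 1 percentage point in an rhNGF arm of 100 or 2 points in a vehicle arm of 50, slightly more if the Safety Set is smaller than planned. The number of such cases cannot be estimated from the documents.

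A reader might go further and infer that the safety results are unreliable or tilted towards one arm. The documents do not support that. TEAE counts, SAE counts and efficacy analyses do not use the AESI flag, the rule makes no reference to treatment, and each case can be found in other planned outputs. The conclusion covers the visible text only.

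**What to change.** Replace the box rule in SAP 8.2.8 with: *an AESI is a serious AE that meets at least one of the five criteria of protocol 11.2.6*. Use the box only to prompt review.

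At the blinded data review meeting already planned before database lock:

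- Review all SAEs, masked, against the five criteria. Do not require the ocular item to be answered yes: protocol 11.2.6 sets no such condition, and a non-ocular AE could cause qualifying visual loss.
- Where a criterion depends on the investigator's opinion or on how long visual loss lasted, resolve it by site query. The meeting cannot supply either.
- If a non-serious AE appears to meet a criterion, send it to the site as a query so that its seriousness is reconciled in the database before lock. Do not reclassify it at the meeting alone. That would either contradict the SAP's statement that every AESI is an SAE or change the SAE counts without a source record.
- Record the decisions in the "BDRM Minutes, which will be finalized before unmasking".

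The cost is a change of SAP wording, one more item at a planned meeting, and a few additional masked data queries.

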10.6 Safety and tolerability evaluation

AEs

Adverse events (AEs) will be coded by System Organ Class (SOC) and Preferred Term (PT), using the Medical Dictionary for Regulatory Activities (MedDRA).

AEs are all events occurring or worsening after the first dose of the IMP.

Individual AEs will be listed in patient data listings. AEs will be summarized by treatment group. The number and percentage of patients with any AE and the number of TEAEs will be tabulated by SOC and PT, seriousness, relationship to treatment and severity.

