11.6 Severity of AEs

The Investigator will grade the severity of any AE using the definitions in the Table below. For each episode, the highest severity grade attained should be reported.

Specifically, the intensity of events should be classified as mild, moderate, or severe.

Table 11.6.1 Intensity (Severity) of the Adverse Event

Mild	Grade 1 - Does not interfere with patient's usual function (awareness of symptoms or signs, but easily tolerated [acceptable]).
Moderate	Grade 2 - Interferes to some extent with patient's usual function (enough discomfort to interfere with usual activity [disturbing]).
Severe	Grade 3 - Interferes significantly with patient's usual function (incapacity to work or to do usual activities [unacceptable])

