4.7 Changes in the Conduct of Study or Planned Analysis compared to protocol/CIP

This SAP implements the subsequent deviations from the analysis specification of the study protocol:

- An updated sample size estimation is given in the SAP to provide a more detailed explanation about the underlying statistical assumptions of the study.
- The RPS InflammDry does not provide specific MMP-9 levels, but is only providing a qualitative assessment “Positive” or “Negative”. As a consequence, the exploratory endpoint “changes in Levels of MMP-9” could not be evaluated. This evaluation will be replaced by providing a shift table displaying qualitative test results of Week 8 vs. Baseline.
- Definition of Screen Failures. In the study protocol (section 10.1.1) a screen failure is defined as patient who is not eligible, i.e. is not respecting all the inclusion/exclusion criteria. According to the study protocol, such patients should not be randomized and enrolled.
To streamline presentation of patient flow for reporting and to extend definition also for protocol deviations, screen failure will be defined as screened patients, who are not randomized. By this, patients, who were randomized although they did not comply with eligibility criteria will not be considered as screen failure. On the contrary, patients, who comply with all eligibility criteria but dropped out from the study before randomization (e.g. due to consent withdrawal) will be considered as screen failure.
- Definition of Safety Set: The protocol defines the Safety Set as all enrolled patients who receive at least one dose of study medication at the study eye. This is adapted to all enrolled patients, who receive at least one dose of study medication irrespective of administered eye, as also study medication given in the non-study eye are also under risk of developing undesired side effects and should therefore be part of safety evaluation.
- Definition of compliance: in section 10.3, the study protocol demands further compliance definitions based on diary card information to investigate compliance with study eye treatment. However, as no eye-specific assessments were recorded on diary card, no such definitions were established.

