- An AE leading to study discontinuation is defined as an AE where in the eCRF section ‘Action regarding Patient’ the box ‘Patient Withdrawn’ is ticked (this should match with the primary reason for early withdrawal of ‘Adverse Event’ on the End of Study eCRF page).
- An AE is classified as ‘Related’ to Study Treatment if the relationship to study medication recorded as ‘Possible’ or ‘Probable’ or ‘Highly Probably’. An AE will be classified as unrelated to study medication if the relationship to study medication was recorded as ‘None’ or ‘Unlikely’. AEs with missing relationship to study treatment will be counted as ‘Related’ to Study Treatment.
- A Fatal AE is defined as an AE where the outcome is recorded as ‘Fatal’.

These definitions will apply accordingly also for the subsequent sub-classes of AEs.

Non Treatment-emergent adverse events (Non-TEAEs)

A Non-TEAE is defined as any AE, which started before the first administration of study treatment. They are identified by the ticked box ‘Before Treatment Period’ in the eCRF Section ‘Did the event occurred.’.

According to the study protocol, both eyes of a patient should be treated. However, there might be the situation, that one eye will not be treated (which will, in fact, be a protocol deviation). For such cases, all ocular events occurring in an eye, which were not treated as indicated on eCRF page 'Study Eye', will also be considered as Non-TEAE irrespective of the timepoint of occurrence.

Treatment-emergent adverse events (TEAEs)

A treatment-emergent adverse event is defined as an AE that started on or after the date of the First Study Treatment Administration. An TEAE will be identified, if

- The eCRF question 'Did the event occurred:' was answered either with 'During Treatment period' or 'During Follow-Up Period'

and

- In case of an ocular event: the affected eye was treated as indicated on the eCRF page 'Study Eye'.

The incidence and frequency of TEAEs will serve as safety endpoint of the study.

TEAEs in the Treatment Period

This will be defined as a TEAE (as defined above) with a start date on or after the date of first study treatment administration and before the Week 8 Visit. It will be identified, if eCRF question 'Did the event occurred:' was answered with 'During Treatment period'.

TEAEs in the Follow-up Period

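### The SAP's treatment-emergent rule is narrower than Protocol 10.6 (no worsening clause, no ocular events in an untreated eye), and SAP 4.7 does not declare the change

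*SAP*

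**What the plan says.** Protocol 10.6 sets the scope of the safety tabulations: "AEs are all events occurring or worsening after the first dose of the IMP". It continues: "The number and percentage of patients with any AE and the number of TEAEs will be tabulated by SOC and PT", with further splits by seriousness, relationship and severity. It makes no distinction by eye. The protocol gives no separate definition of a TEAE.

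SAP 8.2.8 uses onset only: "A treatment-emergent adverse event is defined as an AE that started on or after the date of the First Study Treatment Administration". The complement is "A Non-TEAE is defined as any AE, which started before the first administration of study treatment". Both classes are assigned from the eCRF item on when the event occurred; the onset date is used only if that item is blank.

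For ocular events the SAP adds a second condition: the affected eye must be recorded as treated on the baseline Study Eye page. If it is not, the event "will also be considered as Non-TEAE irrespective of the timepoint of occurrence". The same rule carries over to records with a blank timing item.

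The incidence and frequency of TEAEs is the only safety endpoint listed (Protocol 2.4 and 9.1.4; SAP 4.4). SAP 4.7 lists the departures from the protocol analysis, including the screen-failure, Safety Set and compliance definitions. It does not mention the TEAE definition.

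**The concern.** The SAP narrows the only listed safety endpoint relative to the protocol section it is meant to implement, and does not say so. A reader of the study report would assume that the TEAE tables follow Protocol 10.6.

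The split matters because almost every informative safety table in SAP 10.6.1 is restricted to TEAEs: severity, seriousness, relationship, withdrawal of treatment, study discontinuation, study period, and the comparison with vehicle frequency. In the overview, the special-interest line is restricted in the same way. A serious post-dose ocular event judged related, if it falls in an eye recorded as untreated, would appear in none of these. Nor would an AE that was mild before dosing and became severe on treatment, if it is kept as one record.

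**Working it through.** The documents state no TEAE rate or count, so there is no figure to reproduce. The check sets the rules side by side, identifies which events change class, and then works out what one patient is worth.

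**1. The rules compared**

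| Event | Protocol 10.6 | SAP 8.2.8 |
|---|---|---|
| Starts after first dose, treated eye or non-ocular | counted | TEAE |
| Starts after first dose and later worsens | counted | TEAE |
| Starts before first dose, worsens after it, kept as one record | counted | Non-TEAE |
| Ocular, starts after first dose, eye recorded as untreated | counted | Non-TEAE |

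Only the last two rows differ.

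**2. Can the third row occur?** AEs are recorded from consent (Protocol 11.4), so pre-dose AEs can exist. Protocol 11.6 says: "For each episode, the highest severity grade attained should be reported". An AE that is mild before dosing and severe afterwards can therefore be one record with a pre-dose onset and a severe grade. Three things limit this:
- Consent, randomization, dispensing and the start of treatment are all placed at Day 0 (Protocol 6.1). The window is short, although SAP 8.1 provides for unscheduled visits before first treatment.
- A clinically relevant worsening of a concomitant condition is itself reportable as an AE (Protocol 11.3), presumably with its own post-dose onset.
- An AE that starts on the day of first dose but before the dose meets the SAP's date wording for a TEAE. However, the eCRF timing item takes precedence and would class it as Non-TEAE.

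**3. Can the fourth row occur?** Both eyes should be treated, and the SAP calls one-eye treatment a protocol deviation, but SAP 8.2.5 provides for it. Eye status comes from a baseline question about which eyes are to be treated, so it records intent rather than dosing. Patients dose themselves at home (Protocol 3.1.3), and SAP 4.7 states that the diary holds nothing specific to an eye. An eye that was dosed but not ticked would lose its TEAEs, and the diary could not show it.

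**4. Where the events go.** They appear in the Non-TEAE table, the all-AE line of the overview, the AE listing and the serious AE listing (SAP 10.6.1.1 to 10.6.1.3). They are absent from all TEAE tables. SAP 9.3 also leaves assessments of an untreated eye out of the visual acuity, slit-lamp and external examination summaries, so those tables give no backup.

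**5. What one patient is worth.** Planned arm sizes are 100 and 50 (SAP 4.6). For a patient with no other TEAE, the change in incidence is:
- rhNGF: 1/100 = 1 percentage point
- vehicle: 1/50 = 2 percentage points

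If the patient has another TEAE, overall incidence does not move. The event count and the entry for that term still can.

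**6. Direction.** SAP 10.6.1.2 plans a table of TEAEs at least twice as frequent on active as on vehicle. Hypothetical counts for one term show both directions:
- 4/100 vs 1/50 is 4% vs 2%, ratio 2.0, listed. Lose one rhNGF patient: 3% vs 2%, ratio 1.5, not listed.
- 4/100 vs 2/50 is 4% vs 4%, ratio 1.0, not listed. Lose one vehicle patient: 4% vs 2%, ratio 2.0, listed.

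**The case against.** The other side has a good deal of weight.

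- *The protocol sentence defines AEs, not TEAEs.* True. Reading it as the scope of the TEAE tables is an inference, though a natural one, because the same section tabulates TEAEs.
- *The untreated-eye rule is open and consistent.* It is stated plainly in SAP 8.2.8, confined to a protocol deviation, and matches the convention in SAP 9.3. Whether an event in an eye that received no drug is treatment-emergent is partly convention. This stands, and is why declaring and justifying the exclusion would be an acceptable minimum.
- *Other SAP rules lean towards counting.* Missing severity is taken as severe, missing seriousness as serious, missing relationship as related, and unclassifiable timing as a TEAE in the treatment period. This is correct, but none of these rules brings back the two kinds of event at issue.
- *Nothing is deleted.* Correct; the events are reclassified.

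Stronger readings are tempting but not supported:

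- A reader might infer that the untreated-eye rule contradicts the Safety Set change in SAP 4.7, where patients dosed only in the non-study eye "should therefore be part of safety evaluation". That text concerns an eye that received drug; the rule in 8.2.8 concerns one recorded as not receiving it. The two are compatible.
- A reader might infer that the rules can only make rhNGF look safer. Each can only lower the TEAE count within an arm, but the effect on the comparison depends on which arm loses events, as the hypothetical counts show.
- A reader might want a number of affected patients. The documents give no basis for one.

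**Conclusion.** The point holds as an undeclared difference between the SAP and Protocol 10.6 on the only listed safety endpoint. It covers two narrow classes of event: pre-dose AEs that worsen after dosing within one record, and post-dose ocular events in an eye not recorded as treated at baseline.

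The practical effect is probably small. Few patients are likely to be involved, and the direction of any effect on the comparison between arms is unknown. The size is 1 point of incidence on rhNGF or 2 points on vehicle for each patient whose only TEAE is lost, at the planned arm sizes. The conclusion rests on reading Protocol 10.6 as governing the TEAE tables, and on the eCRF timing item and the baseline eye record deciding the class, as SAP 8.2.8 says they do.

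It is worth correcting before unmasking because the change is cheap and removes a discrepancy that would otherwise carry into the study report.

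**What to change.** 1. In SAP 8.2.8, define a TEAE as an AE that started, or worsened in severity, on or after first dose.
2. Add a recording instruction: a post-dose worsening of a pre-dose AE is entered as a new AE record with its own onset date. The definition cannot work without it, because the AE documentation items in Protocol 11.4 include no date of worsening and Protocol 11.6 keeps one highest grade per episode. The highest-grade rule would then apply within each record.
3. Count post-dose ocular events in an untreated eye as TEAEs, flagged by treated or untreated eye. If the sponsor prefers to keep them out, declare and justify that exclusion in SAP 4.7.

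The cost is slightly more derivation and recording work, including a check of any pre-dose AE records already entered. A few more events may count as TEAEs.
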